### Screening

- Medical history review and demographics
- Complete history and physical examination to include vital signs, blood pressure, body weight, and height.
- Assessment of oxygen saturation
- Baseline clinical laboratory evaluations including complete blood count with differential, platelets, electrolytes, glucose, BUN, serum creatinine, liver function tests, PT/PTT, nt-ProBNP..
- Urine pregnancy test for female of childbearing potential.
- Informed, written consent may be obtained after subject meets eligibility criteria or on day of Study visit (Day 1)

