### **2.2 STUDY DESIGN AND METHODS**

#### **2.2.1. Study Design**

A total of 50 subjects with a confirmed diagnosis of pulmonary hypertension and meeting all inclusion/exclusion criteria will be enrolled in the study which will entail a single right heart catheterization. The study population consisted of subjects with WHO group I PAH (n=20), WHO group II (n=20) and subjects with WHO group III PH (n=10) will receive the following dose escalation paradigm: Each subject will receive a starting dose of 45 mg inhaled nitrite

(AIR001 Inhalation Solution), with one subsequent planned dose escalation of 90 mg inhaled nitrite, based on pulmonary vascular resistance response and safety and tolerability.

Screening (Day 0):

The potential study subjects are followed on a routine basis in the UPMC Heart and Vascular Institute (HVI), Comprehensive Lung Center (CLC) or an inpatient at UPMC Presbyterian, are well known or referred to the study investigator. Initial screening evaluations including physical examination, medical history, and clinical laboratory assessments will be conducted to determine study eligibilities during a routine clinic visit at the UPMC HVI, CLC or inpatient at UPMC Presbyterian. Subjects who meet the inclusion criteria and none of the exclusion criteria will be entered into the study.

Experimental Procedures (Day 1):

The study visit will occur on the same day subjects are scheduled for their clinically indicated right heart catheterization or who volunteer for a research right heart catheterization for this specific study. Subjects on oral background PAH therapy (ETRA or PDE5I) will be instructed to hold their regimen on the day of the study visit.

Subjects will be evaluated for additional medical history, physical examination, vital signs and pulse oximetry since screening. Laboratory testing will be repeated if baseline laboratory values are clinically significant and warrant repeat testing or inadvertently not collected at the screen visit. An echocardiogram with documentation of TRV for estimation of right ventricular systolic pressure and assessment of LV systolic and diastolic function will be performed pre and post nitrite inhalation.

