**2.10 STUDY PROCEDURES**

**2.10.1. Screening**

Screening evaluations to determine eligibility will take place prior to receiving study treatment. The potential study subjects are followed on a routine basis in the UPMC Heart and Vascular (HVI), Comprehensive Lung Center (CLC) or an inpatient at UPMC Presbyterian and are well known or referred to the study investigators. During routine clinical visit, patients who express interest in participation will undergo the screening assessment to determine that all inclusion/exclusion criteria are met prior to receiving the study treatment.

If the patient has had any of the tests done within the 6 months prior to the screening period, they will not be repeated for study purposes. The results collected from these tests and procedure will serve as a baseline for comparison of the subject's overall condition following study treatment. This visit may take up to 2 hours to complete.

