## 2.11. SCHEDULE OF ACTIVITIES (STUDY ASSESSMENT TABLE)

The table below summarizes the protocol procedures that will be performed at screening, during the study treatment, and at follow-up.

Study Phase	Screening	Pre-Treatment	Treatment				Post-Treatment Follow-Up Monitoring	
Visit Type	Outpatient Clinic	Outpatient Cath Lab				Phone Assessment	Outpatient Clinic	
Days on Intervention	Day 0	Day 1				Day 3	Day 30	
Study Procedures		Baseline	Dose 1	Dose 2	Final Measurement			
Informed Consent	X							
Medical History and Demographics	X							
I/E Criteria	X							
Physical Exam	X	X					X	
Vital Signs	X	X					X	
Oxygen Saturation	X	X	X	X	X		X	
Laboratory Tests***	X	X					X	
Urine Pregnancy Test Δ	X	X						
Non-invasive blood pressure measurement		X	X	X				
Right Heart Catheterization (RHC): RA, RV, PA, PCWP, CO/CI (RV measurements at baseline, pre-dose and 60minute interval post last dose AIR001)		X	X	X	X			
Micromanometry		X			X			
Echocardiogram		X			X			
Inhaled NO at 40 ppm if PCWP < 25		X						
PK Sampling*		X	X	X				
metHgb Level§		X	X	X	X			
Plasma cGMP		X	X	X				
Platelet Mitochondrial Analysis		X	X	X				
AE Assessment	X	X	X	X	X	X	X	
Interval History Assessment						X		

Δ Urine pregnancy test will be performed only on female of childbearing potential.

\*\*\* Clinical laboratory tests may be repeated on study visit 1 if screen lab results deemed clinically significant and warrant repeat testing or inadvertently not collected at screen visit.

\* PK Sampling for Nitrite: Blood samples will be obtained at pre-dose and at the end of nebulization at the presumed peak nitrite concentration for each tolerated dosage time points; 15 minutes post inhalation.

§ Methemoglobin (metHgb) levels: will be measured at the following time points: pre-dose, 5, 15, 30 and 60 minutes each dose of AIR001 and at 120 minutes post last dose of AIR001.

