#### WHO Group I, II and III

Age 18 and older;

Able and willing to participate in right heart catheterization;

Evidence of a personally signed and dated informed consent document indicating that the subject has been informed of all pertinent aspects of the study;

Subjects who are willing and able to comply with scheduled visits, treatment plan, laboratory tests, and other study procedures;

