### **4.2 INFORMED CONSENT PROCEDURES**

Informed consent is a process that is initiated prior to the individual's agreeing to participate in the study and continuing throughout the individual's study participation. Extensive discussion of risks and possible benefits of participation in this study will be provided to the subjects and their families. Consent forms describing in detail the study procedures and risks are given to the subject and written documentation of informed consent is required prior to enrolling in the study. Consent forms will be IRB approved and the subject will be asked to read and review the document. Upon reviewing the document, the investigator will explain the research study to the subject and answer any questions that may arise. The subjects will sign the informed consent document prior to being enrolled in the study. The subjects should have the opportunity to discuss the study with their surrogates or think about it prior to agreeing to participate. The subjects may withdraw consent at any time throughout the course of the study. A copy of the informed consent document will be given to the subjects for their records. The rights and welfare of the subjects

will be protected by emphasizing to them that the quality of their medical care will not be adversely affected if they decline to participate in this study.

Prior to performing any of the research study procedures or interventions, subjects must provide informed consent. The investigator will verbally explain the study to the potential subject in a language understandable to subjects, providing all pertinent information (purpose, procedures, risks, benefits, alternatives to participation, etc.), and will allow potential subjects ample opportunity to ask questions to elicit a better understanding of the study. Following this verbal explanation, potential subjects will be provided with a local IRB approved consent form and will be asked to read and review the document. Upon reviewing the document, the investigator will provide adequate opportunity for the subject to consider all options, answer any additional questions the potential subject may have. Every effort will be made to ensure that subjects have comprehended the study information prior to obtaining subject's voluntary agreement to participate.

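### Section 2.10.1 allows written consent after eligibility is settled or on Day 1, which does not agree with Sections 2.11, 3.2 and 4.2 and leaves room for study-only steps before consent

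*Combined protocol and SAP*

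**What the plan says.** Section 2.10.1 lists the screening items: history and demographics, physical examination, oxygen saturation, a laboratory panel that includes nt-ProBNP, and a urine pregnancy test where it applies. The list ends with the timing of consent: "Informed, written consent may be obtained after subject meets eligibility criteria or on day of Study visit (Day 1". The same section says that "patients who express interest in participation will undergo the screening assessment to determine that all inclusion/exclusion criteria are met", and that tests done in the previous 6 months are not redone for the study.

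Other places also bear on when consent is given:

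- **Section 3.2 and the Synopsis**, for all three WHO groups, list as an inclusion criterion: "Evidence of a personally signed and dated informed consent document indicating that the subject has been informed of all pertinent aspects of the study".
- **Section 2.11**: the row "Informed Consent" has one mark, in the Screening (Day 0) column, where the check of inclusion and exclusion criteria is also marked. There is no Day 1 mark and no footnote on timing.
- **Section 4.2**: "written documentation of informed consent is required prior to enrolling in the study", and "Prior to performing any of the research study procedures or interventions, subjects must provide informed consent".

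Section 2.2.1 says that the Day 1 visit coincides either with a clinically indicated catheterization or with one for which the subject volunteers for this study. Subjects on oral ETRA or PDE-5I "will be instructed to hold their regimen on the day of the study visit". The Synopsis has the same instruction.

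**The concern.** The screening list is what staff are likely to work from, and it carries the permissive rule. The stricter rule stands apart, in Section 4.2. Nothing says which governs.

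At stake is subject protection. Under the rule in Section 2.10.1, a patient could have blood or urine taken for no reason other than study eligibility, or be told to change a medicine for study purposes, before signing anything. There is also a record-keeping consequence: under the Day 1 option, a subject can lack one inclusion criterion when the Schedule says the criteria are checked. Consent timing enters no power or analysis calculation, so the primary comparison of pulmonary vascular resistance does not depend on it.

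**Working it through.** No arithmetic applies, so the check compares the texts.

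1. **Section 2.10.1 against Section 3.2.** Signed consent is one of the eligibility criteria. Read literally, a subject cannot meet those criteria and sign afterwards. The sentence works only if it means the clinical criteria, which it does not say.

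2. **Section 2.10.1 against Section 2.11.** The Schedule puts consent at Screening alone, and Section 2.10.1 also permits Day 1. The Schedule gives the visit but not the order within it. Even where consent is taken at Screening, nothing in the table places it before the laboratory or pregnancy tests in the same column.

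3. **Section 2.10.1 against Section 4.2.** Section 4.2 puts consent before any research procedure. Whether the two collide depends on whether anything done before signature is a research step.
   - *Tests.* Section 2.10.1 ties the screening assessment to interest in the study and to checking its criteria. Sparing recent tests from repetition for study purposes implies that a test with no recent result is done for study purposes. Section 2.12.6 describes the laboratory panel as serving baseline and follow-up comparison. A laboratory or pregnancy test with no recent result can therefore be study-only, and Section 2.10.1 lets it come before consent.
   - *Medicine hold.* The Synopsis and Section 2.2.1 present the hold as an instruction that applies on the study day. No time is given for issuing it. An instruction covering that day would ordinarily be given before arrival; that is an inference. If so, and if consent is deferred to Day 1, the instruction comes first. The case is clearest for those who volunteer for a research-only catheterization, because no clinical procedure exists to which the hold could be attributed.

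4. **Who could be affected.** The consent line applies to everyone, so the ceiling is the planned 50 subjects. The floor is 0, reached if every subject's eligibility rests on routine or re-used results and no study instruction precedes signature. The documents give neither the proportion with a study-only screening test nor the proportion on oral ETRA or PDE-5I, so the range cannot be narrowed.

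**The case against.** The best reply is that Section 2.10.1 is permissive and Section 4.2 is mandatory, so both can be obeyed together. The protocol largely describes how:

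- patients are already followed in the clinics and are screened at a routine visit (Sections 2.2.1 and 2.10.1);
- results from the previous 6 months are re-used (Sections 2.10.1 and 2.12.6);
- the investigator may review records to find candidates (Section 4.1);
- routine laboratory tests are treated as routine care (Section 7.1);
- laboratory tests missed at screening may be obtained on Day 1 ahead of research procedures (Section 2.10.2), wording that separates such tests from research.

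This stands to a large extent. A reader might infer that following Section 2.10.1 necessarily breaches Section 4.2. The documents do not support that: where eligibility rests on routine information and consent is signed before research begins, there is no breach. The reply also softens the literal conflict with Section 3.2, since a reader of a checklist would probably take eligibility to mean the clinical criteria.

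On the hold, Section 2.2.1 describes it under the Day 1 procedures, after saying that eligible subjects are entered into the study. Under Sections 3.2 and 4.2 such subjects would already have signed. A hold before consent is thus possible under the deferred option, but it is not shown.

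The reply does not remove the gap. Section 2.10.1 nowhere limits pre-consent activity to routine care, and the Schedule still disagrees with it about Day 1.

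**Conclusion.** The point holds as an internal inconsistency with a real but limited consequence. Section 2.10.1 does not agree with Section 2.11, with the consent criterion in Section 3.2 and the Synopsis, or with the order set in Section 4.2. As written, it allows a test done only for study eligibility to precede consent. It may also allow the study's hold instruction to do so, on the assumption that the instruction is given before a Day 1 signature. The number affected is unknown, and 50 is a ceiling rather than an estimate. The plan should be amended.

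Two further inferences are tempting but not supported:

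- **That sedation may precede consent on Day 1.** Section 5.1 names sedatives in a list of risks and sets no sequence. For a research catheterization, Section 4.2 already requires consent before the procedure. Silence in Section 2.10.1 does not override that.
- **That screening data would be unusable.** No section says so, and much of the screening data may come from routine care.

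**What to change.** Reword the consent line in Section 2.10.1 to say that:

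- written consent is obtained before any test done only for the study and before any study instruction about background medicines;
- consent on Day 1 is allowed only where nothing study-specific has been done before it, and it then precedes every Day 1 research procedure;
- record review (Section 4.1) and re-use of routine results (Section 2.10.1) may continue before consent.

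Add a footnote to the consent row of Section 2.11 giving this order and the condition for Day 1 consent. In Section 3.2 and the Synopsis, make clear that the clinical criteria may be pre-assessed from routine information, with the consent criterion met at the time Section 4.2 requires. These changes concern only the order of consent. They take no position on whether or how background medicines should be held.

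The cost is a short amendment. Consent will be discussed with some patients who later fail screening, and the site loses some freedom to defer consent to Day 1. Where screening is wholly routine care and no study instruction has been given, the Day 1 option remains.

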### **2.10.2. Experimental procedures (Day 1)**

Subjects who meet the inclusion criteria and none of the exclusion criteria will receive the study treatment of inhaled nitrite. The study will take place at UPMC Presbyterian Hospital, 3rd FL Catheterization Laboratory, and may take up to 6 hours to complete.

#### Pre-Dose: Baseline

- Physical examination to include vital signs, blood pressure, weight and oxygen saturation
- Laboratory testing that clinically warrants repeating testing or inadvertently not collected for screening may be obtained prior to research procedures
- Echocardiogram
- Non-invasive blood pressure measurement
- Right Heart Catheterization (RHC)-RA, RV, PA, pulmonary capillary wedge pressure (PCWP), CO/CI
- Inhaled NO testing at 40 ppm if PCWP < 25 with hemodynamic response recorded (RA, PA, PCWP, CO/CI)
- Micromanometry to record high fidelity pressure signals with simultaneous flow velocity from transthoracic echocardiographic ultrasound for the measurement of pulmonary arterial input impedance. Micromanometer pressure catheter is inserted via the Swann-Ganz catheter distal port.
- Repeat 2nd baseline hemodynamic measurement: RA, RV, PA, PCWP. CO/CI
- Pre-dose baseline PK, cGMP and platelet mitochondrial samples
- Pre-dose methemoglobin measurement

#### AIR001 Dose 1 45 mg Nebulized

- Non-invasive blood pressure measurement
- PK, cGMP and platelet mitochondrial samples (approx. 15 minutes after nebulization)
- RA, PA, PCWP, CO/CI (approx. 15, 30, 45, 60 minutes after nebulization)
- AE assessment
- Methemoglobin (MetHgb) measurements (approx. 5, 15, 30, 60 minutes after nebulization)

#### AIR001 Dose 2 90mg Nebulized

- Non-invasive blood pressure measurement
- PK, cGMP and platelet mitochondrial samples (approx. 15 minutes after nebulization)
- RA, PA, PCWP, CO/CI (approx. 15, 30, 45, 60 minutes after nebulization)
- AE assessment
- MetHgb measurements (approx. 5, 15, 30, 60 minutes after nebulization)

#### Final Measurements:

- Includes 60 minute hemodynamic measurements (RA, PA, PCWP, CO/CI) from last tolerated AIR001 dose
- RV measurement
- AE assessment
- Micromanometry to record high fidelity pressure signals with simultaneous flow velocity from transthoracic echocardiographic ultrasound for the measurement of pulmonary arterial input impedance. Micromanometer pressure catheter is inserted via the Swann-Ganz catheter distal port.
- Echocardiogram
- SpO2 and MetHgb measurements at approx. 120 minutes post last tolerable dose

#### PK Sampling for Nitrite/Nitrate:

- Blood samples for PK analysis may be collected at pre-dose and at the end of nebulization at the presumed peak nitrite concentration for each tolerated dosage time points; approximately 15 minutes post inhalation.

#### Methemoglobin (metHgb) levels:

- MetHgb levels will be recorded via co-oximetry at the following approximate time points: pre-dose, 5, 15, 30, 60 minutes after each dose of AIR001 and at 120 minutes post last dose of AIR001. Venous methemoglobin levels will be assessed as clinically indicated at the discretion of the investigator. Due to circumstances unknown, co-oximetry may not pick up methemoglobin readings. In those instances, venous methemoglobin levels will be collected at approximate 30 and 45 minute post inhalation time points.

#### **2.10.3. Follow-up monitoring (Day 3)- Telephone Assessment**

The interval telephone assessment should be completed as close to the scheduled visit date as possible. However, a variance of 2 days will be allowed for the follow-up monitoring to facilitate scheduling or to account for weekends or holidays.

Subjects will be contacted by the study investigator and/or the study coordinator for a follow-up assessment by telephone to assess for symptoms potentially related to adverse effects of

study drug, review of medication changes, and interval medical or surgical histories including emergency or physician office visits. This phone assessment may last about 30 minutes.

- Interval history assessment
- AE assessment

#### **2.10.4. Follow-up monitoring (Day 30 +/- 5 day window)- Outpatient Clinic Assessment**

Outpatient visits should be completed as close to the scheduled visit dates as possible. However, a variance of 5 days will be allowed for the follow-up monitoring to facilitate scheduling or to account for weekends or holidays. This visit will take place at the UPMC HVI and CLC outpatient clinic, and may take up to 2 hours to complete.

- Physical examination to include vital signs, blood pressure and oxygen saturation
- Clinical laboratory evaluations
- AE assessment

In addition to these formal evaluations, subjects will be encouraged to immediately contact the study coordinator and/or the investigators with questions, concerns, or to report new symptoms that occur during their study participation. If appropriate, based upon the evaluation, medical treatments will be provided to subjects, including appropriate referral to physicians or other services at the UPMC.

Any clinically significant adverse event, laboratory test or physical examination observed during final assessments will be followed as medically appropriate until resolved or explained.

## 2.11. SCHEDULE OF ACTIVITIES (STUDY ASSESSMENT TABLE)

The table below summarizes the protocol procedures that will be performed at screening, during the study treatment, and at follow-up.

Study Phase	Screening	Pre-Treatment	Treatment				Post-Treatment Follow-Up Monitoring	
Visit Type	Outpatient Clinic	Outpatient Cath Lab				Phone Assessment	Outpatient Clinic	
Days on Intervention	Day 0	Day 1				Day 3	Day 30	
Study Procedures		Baseline	Dose 1	Dose 2	Final Measurement			
Informed Consent	X							
Medical History and Demographics	X							
I/E Criteria	X							
Physical Exam	X	X					X	
Vital Signs	X	X					X	
Oxygen Saturation	X	X	X	X	X		X	
Laboratory Tests***	X	X					X	
Urine Pregnancy Test Δ	X	X						
Non-invasive blood pressure measurement		X	X	X				
Right Heart Catheterization (RHC): RA, RV, PA, PCWP, CO/CI (RV measurements at baseline, pre-dose and 60minute interval post last dose AIR001)		X	X	X	X			
Micromanometry		X			X			
Echocardiogram		X			X			
Inhaled NO at 40 ppm if PCWP < 25		X						
PK Sampling*		X	X	X				
metHgb Level§		X	X	X	X			
Plasma cGMP		X	X	X				
Platelet Mitochondrial Analysis		X	X	X				
AE Assessment	X	X	X	X	X	X	X	
Interval History Assessment						X		

Δ Urine pregnancy test will be performed only on female of childbearing potential.

\*\*\* Clinical laboratory tests may be repeated on study visit 1 if screen lab results deemed clinically significant and warrant repeat testing or inadvertently not collected at screen visit.

\* PK Sampling for Nitrite: Blood samples will be obtained at pre-dose and at the end of nebulization at the presumed peak nitrite concentration for each tolerated dosage time points; 15 minutes post inhalation.

§ Methemoglobin (metHgb) levels: will be measured at the following time points: pre-dose, 5, 15, 30 and 60 minutes each dose of AIR001 and at 120 minutes post last dose of AIR001.

